**Table 9 Reporting Time Periods and Time Frames for Adverse Events and Other Reportable Safety Events**

Type of Event	Reporting Time Period: Consent to Randomization/Allocation	Reporting Time Period: Randomization/Allocation through Protocol-specified Follow-up Period	Reporting Time Period: After the Protocol-specified Follow-up Period	Time Frame to Report Event and Follow-up Information to Merck:
Serious Adverse Event (SAE) including Cancer and Overdose	Report if: - due to protocol-specified intervention - causes exclusion - participant is receiving placebo run-in or other run-in treatment	Report all	Report if: - drug/vaccine related. (Follow ongoing to outcome)	Within 2 business days but no longer than 3 calendar days of receipt of information
Pregnancy/Lactation Exposure	Report if:  - participant has been exposed to any protocol-specified intervention (eg, procedure, washout or run-in treatment including placebo run-in)  Exception: A positive pregnancy test at the time of initial screening is not a reportable event.	Report all	Previously reported – Follow to completion/termination; report outcome	Within 2 business days but no longer than 3 calendar days of receipt of information
Event of Clinical Interest (require regulatory reporting)	Report if: - due to intervention - causes exclusion	Report - potential drug-induced liver injury (DILI) - require regulatory reporting	Not required	Within 2 business days but no longer than 3 calendar days of receipt of information

### **6.1.2 Method of Detecting AEs, SAEs, and Other Reportable Safety Events**

Care will be taken not to introduce bias when detecting AEs and/or SAEs and other reportable safety events. Open-ended and nonleading verbal questioning of the participant is the preferred method to inquire about AE occurrence.

### **6.1.3 Follow-up of AE, SAE, and Other Reportable Safety Event Information**

After the initial AE/SAE report, the investigator is required to proactively follow each participant at subsequent visits/contacts. All AEs, SAEs, and other reportable safety events including pregnancy and exposure during breastfeeding, events of clinical interest (ECIs), cancer, and overdose will be followed until resolution, stabilization, until the event is otherwise explained, or the participant is lost to follow-up. In addition, the investigator will make every attempt to follow all nonserious AEs that occur in allocated or randomized participants for outcome. Further information on follow-up procedures is given in Appendix 5.

### **6.1.4 Sponsor Responsibility for Reporting Adverse Events**

All Adverse Events will be reported to regulatory authorities, IRB/IECs and investigators in accordance with all applicable country specific regulatory requirements, global laws and regulations.

### **6.1.5 Pregnancy and Exposure During Breastfeeding**

Although pregnancy and infant exposure during breastfeeding are not considered AEs, any pregnancy or infant exposure during breastfeeding in a participant (spontaneously reported to the investigator or their designee) that occurs during the study are reportable to the Sponsor.

All reported pregnancies must be followed to the completion/termination of the pregnancy.

Any pregnancy complication will be reported as an AE or SAE.

The medical reason (example: maternal health or fetal disease) for an elective termination of a pregnancy will be reported as an AE or SAE. Prenatal testing showing fetus will be born with severe abnormalities/congenital anomalies that leads to an elective termination of a pregnancy will be reported as an SAE for the fetus.

Pregnancy outcomes of ectopic pregnancy, spontaneous abortion, missed abortion, benign hydatidiform mole, blighted ovum, fetal death, intrauterine death, miscarriage, and stillbirth must be reported as serious events (Important Medical Events). If the pregnancy continues to term, the outcome (health of infant) must also be reported

### **6.1.6 Events of Clinical Interest (ECIs)**

Selected nonserious and SAEs are also known as ECIs and must be reported to Merck.

Events of clinical interest for this study include:

1. An overdose of pembrolizumab that is not associated with clinical symptoms or abnormal laboratory results. For purposes of this study, an overdose of pembrolizumab will be defined as any dose of 1,000 mg or greater. No specific information is available on the treatment of overdose of pembrolizumab. In the event of overdose, the participant should be observed closely for signs of toxicity. Appropriate supportive treatment should be provided if clinically indicated.
2. An elevated AST or ALT lab value that is greater than or equal to 3X the upper limit of normal and an elevated total bilirubin lab value that is greater than or equal to 2X the upper limit of normal and, at the same time, an alkaline phosphatase lab value that is less than 2X the upper limit of normal, as determined by way of protocol-specified laboratory testing or unscheduled laboratory testing.\*

\*Note: These criteria are based upon available regulatory guidance documents. The purpose of the criteria is to specify a threshold of abnormal hepatic tests that may require an additional evaluation for an underlying etiology.

## 7.0 STATISTICAL ANALYSIS PLAN

We will simultaneously monitor efficacy and toxicity using the Bayesian optimal phase 2 (BOP2) design (Zhou, Lee and Yuan, 2017). Specifically, let  $n$  denote the interim sample size, and  $N$  denote the maximum sample size. Let  $Y_{eff}$  and  $Y_{tox}$  denote the binary efficacy and toxicity endpoints, with  $Y_{eff} = 1$  and  $Y_{tox} = 1$  indicating that patients experience efficacy and toxicity, respectively. We assume that the joint distribution of  $(Y_{eff}, Y_{tox})$  follows a multinomial distribution with four elementary outcomes:  $(Y_{eff}, Y_{tox}) = (1, 1), (1, 0), (0, 1)$  and  $(0, 0)$ . Let  $\mathbf{p} = (P_{11}, P_{10}, P_{01}, P_{00})$  denote the probabilities of observing the four outcomes, and let  $p_{eff} = Pr(Y_{eff} = 1)$ ,  $p_{tox} = Pr(Y_{tox} = 1)$  and  $p_{eff,tox} = Pr(Y_{eff} = 1, Y_{tox} = 1)$ . When efficacy and toxicity endpoints are monitored separately, the joint distribution reduced to marginal distribution of efficacy and marginal distribution of toxicity, respectively. For trial monitoring and decisions, extreme toxicities (TOX) will be defined as any grade 3 or higher adverse event that is possibly, probably, or related to therapy received on this protocol. Any grade 3 or higher adverse event that is potentially treatable with steroids or hormonal replacement will only count as an extreme toxicity if it does not improve to grade 1 or better within 2 weeks of therapy.

The treatment is deemed unacceptable if  $p_{eff} \leq 0.23$  or  $p_{tox} > 0.5$ . Thus, we will stop enrolling patients and claim that the treatment is unacceptable if

$$Pr(p_{eff} > 0.23 | data) < \lambda \left( \frac{n}{N} \right)^\alpha,$$

or

$$Pr(p_{tox} \leq 0.5 | data) < \lambda \left( \frac{n}{N} \right)^{\alpha/3},$$

where  $\lambda=0.5$  and  $\alpha=1$  are design parameters optimized to maximize the study power, i.e., probability of correctly concluding an efficacious and safe treatment as acceptable when  $p_{eff} = 0.3$ ,  $p_{tox} = 0.3$  and  $p_{efftox} = 0.18$ , while controlling that the probability of incorrectly claiming an inefficacious and toxic treatment, i.e., type I error, with  $p_{eff} = 0.23$ ,  $p_{tox} = 0.5$  and  $p_{efftox} = 0.15$ , to 9.5%. Note that in the safety stopping rule, the original publication of the design used the probability cutoff  $\lambda(n/N)^\alpha$ , here the attenuation factor 3 is added (i.e.,  $\alpha/3$ ) to obtain stricter interim stopping boundaries to enhance safety.

For the purposes of interim monitoring, toxicities and responses will be monitored for 24 weeks post start of the combination therapy.

This optimization is performed assuming a vague Dirichlet prior  $Dir(0.15, 0.08, 0.35, 0.42)$  for  $\mathbf{p}$ . The prior is chosen such that it corresponds to a prior effective sample size of 1 patient, and the prior estimates of  $p_{eff}$  and  $p_{tox}$  match the values specified when the treatment is unacceptable. The above decision rule leads to the following optimal stopping boundaries:

*Table 1: Optimized stopping boundaries*

# patients treated	Stop if # response <=	OR # toxicity	
		<=	>=
10	0	6	
20	3	11	
35	7	18	
50	11	25	

When the total number of patients reaches the maximum sample size of 50, we conclude that the treatment is acceptable if the number of responses are greater than 11, and the number of toxicities are less than 25; otherwise we conclude that the treatment is unacceptable. The go/no-go criteria in Table 1 are non-binding.

Below are the operating characteristics of the design based on 10000 simulations using the BOP2 web application (BOP2 V1.4.7.0), which is available at <http://www.trialdesign.org>.

*Table 2: Operating characteristics*

Scenario	Pr(Eff)	Pr(Tox)	Pr(Eff & Tox)	Early Stopping (%)	Claim Acceptable (%)	Average Sample Size
1	0.23	0.5	0.15	83.15	9.47	23.0
2	0.30	0.3	0.18	24.46	71.38	42.9

ORR will be summarized with a 95% confidence interval (Clopper-Pearson exact method).

**Analysis of Secondary Endpoints:** OS and PFS will be analyzed using Kaplan-Meier survival curves. T-tests and dot plots will be used to associated mitotane levels (specify time of measurement) with overall response. Adverse events will be summarized with frequencies tables. Highest grade adverse event will be determined for each subject and the count of all adverse events and related adverse events will be computed.

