#### **5.2.4 Dose Modification and toxicity management for immune-related AEs associated with pembrolizumab and IO combination partners**

AEs associated with pembrolizumab or IO/IO combination exposure, may represent an immunologic etiology. These immune-related AEs (irAEs) may occur shortly after the first dose or several months after the last dose of pembrolizumab/combination treatment and may affect more than one body system simultaneously. Therefore, early recognition and initiation of treatment is critical to reduce complications. Based on existing clinical study data, most irAEs were reversible and could be managed with interruptions of pembrolizumab/combination treatment, administration of corticosteroids and/or other supportive care. For suspected irAEs, ensure adequate evaluation to confirm etiology or exclude other causes. Additional procedures or tests such as bronchoscopy, endoscopy, skin biopsy may be included as part of the evaluation. Dose modification and toxicity management guidelines for irAEs associated with pembrolizumab/combination treatment are provided in Table 6.

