#### **Restarting Study Interventions:**

Participants may restart pembrolizumab and MT as described below.

- If the toxicities do resolve and conditions are aligned with what is defined in [Table 6], the study interventions may be restarted at the discretion of the investigator.

**Table 6 Dose modification and toxicity management guidelines for immune-related AEs associated with pembrolizumab and IO combination partners**

General instructions:				

 
1. Severe and life-threatening irAEs should be treated with IV corticosteroids followed by oral steroids. Other immunosuppressive treatment should begin if the irAEs are not controlled by corticosteroids.
 
2. All IO treatments must be permanently discontinued if the irAE does not resolve or the corticosteroid dose is not <math>\leq</math>10 mg/day within 12 weeks of the last study intervention treatment.
 
3. The corticosteroid taper should begin when the irAE is <math>\leq</math> Grade 1 and continue at least 4 weeks.
 
4. If IO treatments have been withheld, study intervention may resume after the irAE decreased to <math>\leq</math> Grade 1 after corticosteroid taper.
 
				

irAEs	Toxicity Grade (CTCAE v5.0)	Action With Pembrolizumab + all IO Drugs	Corticosteroid and/or Other Therapies	Monitoring and Follow-up
Pneumonitis	Grade 2	Withhold	
 
• Administer corticosteroids (initial dose of 1 to 2 mg/kg prednisone or equivalent) followed by taper
 
• Add prophylactic antibiotics for opportunistic infections
 
	
 
• Monitor participants for signs and symptoms of pneumonitis
 
• Evaluate participants with suspected pneumonitis with radiographic imaging and initiate corticosteroid treatment
 

	Recurrent Grade 2, Grade 3 or 4	Permanently discontinue		
Diarrhea/Colitis	Grade 2 or 3	Withhold	
 
• Administer corticosteroids (initial dose of 1 to 2 mg/kg prednisone or equivalent) followed by taper
 
	
 
• Monitor participants for signs and symptoms of enterocolitis (ie, diarrhea, abdominal pain, blood or mucus in stool with or without fever)
 

irAEs	Toxicity Grade (CTCAE v5.0)	Action With Pembrolizumab + all IO Drugs	Corticosteroid and/or Other Therapies	Monitoring and Follow-up

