## **5.6 Participant Discontinuation Criteria**

Discontinuation of study intervention does not represent withdrawal from the study.

As certain data on clinical events beyond study intervention discontinuation may be important to the study, they must be collected through the participant's last scheduled follow-up, even if the participant has discontinued study intervention. Therefore, all participants who discontinue study intervention prior to completion of the protocol-specified treatment period will still continue to be monitored in this study and participate in the study visits and procedures as specified in Section 2.2 unless the participant has withdrawn from the study (Section 5.7).

Participants may discontinue study intervention at any time for any reason or be discontinued from the study intervention at the discretion of the investigator should any untoward effect occur. In addition, a participant may be discontinued from study intervention by the investigator or the Sponsor if study intervention is inappropriate, the study plan is violated, or for administrative and/or other safety reasons.

A participant must be discontinued from study treatment but continue to be monitored in the study for any of the following reasons:

- The participant or participant's legally acceptable representative requests to discontinue study intervention
- After prolonged study intervention interruption that prohibits restarting study intervention if agreed upon with the Sponsor
- Radiographic disease progression outlined in Section 6.1.4.

- Any progression or recurrence of malignancy, or any occurrence of another malignancy that requires active treatment
- Any study intervention-related toxicity specified as a reason for permanent discontinuation as defined in the guidelines for dose modification due to AEs in Section 5.2.4.
- The participant has a medical condition or personal circumstance which, in the opinion of the investigator and/or sponsor, placed the participant at unnecessary risk from continued administration of study treatment.
- The participant has a confirmed positive serum pregnancy test

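### The recovery exemption in the TOX definition has no upper grade, so a related grade 4 immune event that ends pembrolizumab under Table 6 can score as no toxicity in the only quantified safety rule

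*Combined protocol and SAP*

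**What the plan says.** Section 7.0 first defines the endpoint broadly: "extreme toxicities (TOX) will be defined as any grade 3 or higher adverse event that is possibly, probably, or related to therapy received". It then narrows it: "Any grade 3 or higher adverse event that is potentially treatable with steroids or hormonal replacement will only count as an extreme toxicity". What brings such an event back into the count is a recovery condition, worded "if it does not improve to grade 1 or better within 2 weeks of therapy". The exemption covers grade 3 and above without a ceiling. It asks only that the event be potentially treatable with steroids or hormones, not that either was given. It does not say which therapy starts the two-week clock.

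This endpoint feeds the toxicity boundary at 10, 20, 35 and 50 patients and the conclusion at 50. The stopping criteria are stated to be non-binding.

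Table 6 (Section 5.2.4) says of immune-related events: "Severe and life-threatening irAEs should be treated with IV corticosteroids followed by oral steroids". It also lists the events for which pembrolizumab is permanently discontinued. The pneumonitis row, for example, reads "Recurrent Grade 2, Grade 3 or 4". Section 5.6 makes such discontinuation mandatory: "Any study intervention-related toxicity specified as a reason for permanent discontinuation" is one of its listed reasons.

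**The concern.** Two parts of the same document grade the same event very differently. Under Table 6, a grade 4 steroid-treated immune event is in most rows severe enough that the patient may never receive pembrolizumab again. Under Section 7.0, the same event scores zero if it reaches grade 1 within two weeks.

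The exempt class need not be marginal. Section 5.2.4 says that "most irAEs were reversible and could be managed with interruptions of pembrolizumab/combination treatment, administration of corticosteroids and/or other supportive care", although it gives no rate of recovery by two weeks. Recovery to grade 1 is also not the end of treatment: Table 6 starts the steroid taper at that point and runs it for at least four weeks.

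Section 4.2.1 notes that the combination has not been studied prospectively. Section 7.0 holds the only safety rule with numbers attached. The other protections are a termination criterion without a threshold (Section 5.9) and descriptive adverse event tables. Events removed from TOX therefore have no quantified trigger anywhere.

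**Working it through.** **1. The passages side by side.** For a related grade 4 event that reaches grade 1 within two weeks:

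| Event | Table 6: corticosteroids | Table 6: pembrolizumab | Section 7.0 score |
|---|---|---|---|
| Pneumonitis | yes | permanently discontinued | not TOX |
| Diarrhea/colitis | yes | permanently discontinued | not TOX |
| AST/ALT or bilirubin | yes | permanently discontinued | not TOX |
| Nephritis | yes | permanently discontinued | not TOX |
| Neurological | yes, by severity | permanently discontinued | not TOX |
| Myocarditis | yes, by severity | permanently discontinued | not TOX |

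The score is per patient, so someone with a separate qualifying event still counts. For endocrine events, Table 6 continues, withholds or leaves the decision to the physician. It does not mandate discontinuation.

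**2. Reproducing the plan's design.** Inputs from Section 7.0: prior Dir(0.15, 0.08, 0.35, 0.42), λ = 0.5, α = 1, N = 50. The toxicity margin of the prior is Beta(0.15 + 0.35, 0.08 + 0.42) = Beta(0.5, 0.5). With x toxicities in n patients, stop if Pr(p_tox ≤ 0.5) under Beta(0.5 + x, 0.5 + n − x) is below 0.5(n/50)^(1/3).

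| n | Boundary x | Posterior probability | Cutoff |
|---|---|---|---|
| 10 | 6 | 0.265 | 0.292 |
| 20 | 11 | 0.328 | 0.368 |
| 35 | 18 | 0.433 | 0.444 |
| 50 | 25 | 0.500 | 0.500 |

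These are the printed boundaries 6/11/18/25; the last is a tie that the plan treats as a stop. An exact multinomial recursion through the four looks, with efficacy stops at ≤ 0/3/7/11, gives 9.56% acceptable in scenario 1 (plan 9.47%) and 71.9% in scenario 2 (plan 71.38%). Both agree within about the simulation error of 10,000 runs (standard errors about 0.3 and 0.45 points). The arithmetic of the rule is sound; the question is what it counts.

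**3. What one exempt patient does.** At n = 10, six toxicities stop the trial (0.265 < 0.292). If one of the six had only an exempt grade 4 event, the count is five, the posterior probability is 0.500 and enrollment continues.

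**4. Sensitivity to the whole exemption.** Counted rate = true related grade ≥ 3 rate × (1 − share of affected patients with only exempt events). Both inputs are assumptions. Probability that the toxicity boundary is crossed at any look:

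| True rate | 0% exempt | 20% exempt | 40% exempt |
|---|---|---|---|
| 50% | 70.9% | 27.4% | 5.8% |
| 60% | 96.8% | 62.1% | 15.6% |
| 70% | 99.95% | 90.5% | 35.0% |

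At low rates little changes. Section 4.2.1 cites 13% serious adverse events on pembrolizumab alone; a 13% rate crosses with probability 0.06% even if fully counted. At the plan's target of 30%, with p_eff 0.30 and toxicity independent of response, exempting 20% gives a counted rate of 0.30 × 0.80 = 24% and moves the probability of declaring the treatment acceptable only from 72.8% to 75.9%.

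**5. Cost of counting more.** Same recursion, p_eff 0.30, independence, boundaries unchanged. Scenario 2 gives 71.9% rather than 72.8% because it uses a joint probability of 0.18 instead of 0.30 × 0.30 = 0.09.

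| Counted TOX rate | Declared acceptable | Stopped early |
|---|---|---|
| 30% | 72.8% | 23% |
| 33% | 69.7% | 26% |
| 35% | 66.9% | 29% |
| 40% | 56.1% | 39% |

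**The case against.** The exemption is an openly stated definition, not a slip. Table 6 decides whether one patient may be re-exposed, while TOX judges the regimen as a whole, and the two may properly differ. Disregarding brief steroid-responsive events is a recognisable choice for an immunotherapy combination. Fatal events, slow-recovering events and related grade 3+ events outside the steroid- or hormone-treatable class all still count. The criteria are non-binding, serious events are reported promptly, and Section 5.9 allows termination for the severity of adverse reactions. All of this stands, and it rules out calling the definition an error.

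A reader might infer from the sensitivity table that the rule misses the most serious immune toxicities and would often pass a dangerous regimen. The documents do not support that. True rates of 50% to 70% and the exempt shares are assumed. The 0%-exempt column counts every related grade 3+ event, which is not what the fix would do. Counted rates at or below 50% also lie within the plan's own limit.

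A reader might also infer that the exemption defeats the attenuated exponent, added "to obtain stricter interim stopping boundaries to enhance safety". That clause concerns the interim cutoffs, and it works: without it the interim toxicity boundaries would be 8/12/19 instead of 6/11/18. It says nothing about which events count.

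What the objection does not supply is a reason for extending the exemption to grade 4. The plan gives none.

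**Conclusion.** The concern holds in a limited form. As written, a related grade 4 steroid-treatable immune event that recovers within two weeks is scored as no toxicity, even where Table 6 ends pembrolizumab. That follows from the text alone. Its effect on the trial's decisions cannot be sized, because the documents give neither the share of patients with only exempt events nor a toxicity rate for this combination. It is negligible near 13%, small near 30%, and potentially large only if true toxicity is near or above the 50% limit.

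It is tempting to go further and require every event that triggers discontinuation under Table 6 to count, including grade 2 myocarditis or recurrent grade 2 pneumonitis and all such grade 3 events. The documents do not require that. It would undo most of a deliberate exemption, bring grade 2 events into an endpoint defined from grade 3, and could cost real power (56.1% at a counted rate of 40%). That is a trade-off for the sponsor. Capping the exemption below grade 4 is a cheap improvement, not the repair of a design error.

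**What to change.** Amend the exemption sentence in Section 7.0 so that, for monitoring:

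- recovery within two weeks exempts grade 3 events only, plus endocrine events managed by hormone replacement for which Table 6 does not mandate discontinuation;
- related grade 4 steroid-treated immune events count whatever their recovery;
- the scoring of recovering grade 3 events that lead to permanent discontinuation is stated explicitly, and their number is reported at each look;
- the therapy that starts the two-week clock is named.

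Keep the boundaries and looks, and leave Table 6 and all other clinical management rules untouched.

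The cost is a few lines of text. Grade, causality and action taken are already recorded (Section 6.1.2.1). The statistical price is slightly more early stopping and slightly lower power. If the counted rate rose from 30% to 33%, an assumed rise of three patients in 100, the probability of declaring an effective and tolerable treatment acceptable would fall by 72.8 − 69.7 = 3.1 points. The sponsor should rerun the Section 7.0 operating characteristics with its own estimate of that rise.

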	Grade 3 or 4	Withhold or permanently discontinue d		
Hypothyroidism	Grade 2, 3 or 4	Continue	
 
Initiate thyroid replacement hormones (eg, levothyroxine or liothyronine) per standard of care
 
	
 
Monitor for signs and symptoms of thyroid disorders
 

Nephritis: grading according to increased creatinine or acute kidney injury	Grade 2	Withhold	
 
Administer corticosteroids (prednisone 1 to 2 mg/kg or equivalent) followed by taper
 
	
 
Monitor changes of renal function
 

	Grade 3 or 4	Permanently discontinue		

irAEs	Toxicity Grade (CTCAE v5.0)	Action With Pembrolizumab + all IO Drugs	Corticosteroid and/or Other Therapies	Monitoring and Follow-up
Neurological Toxicities	Grade 2	Withhold	
 
Based on severity of AE administer corticosteroids
 
	
 
Ensure adequate evaluation to confirm etiology and/or exclude other causes
 

	Grade 3 or 4	Permanently discontinue		
Myocarditis	Asymptomatic cardiac enzyme elevation with clinical suspicion of myocarditis (previously CTCAE v4.0 Grade 1)	Withhold	
 
Based on severity of AE administer corticosteroids
 
	
 
Ensure adequate evaluation to confirm etiology and/or exclude other causes
 

	Grade 2, 3 or 4	Permanently discontinue		
Exfoliative Dermatologic Conditions	Suspected SJS, TEN, or DRESS	Withhold	
 
Based on severity of AE administer corticosteroids
 
	
 
Ensure adequate evaluation to confirm etiology or exclude other causes
 

	Confirmed SJS, TEN, or DRESS	Permanently discontinue		
All Other irAEs	Persistent Grade 2	Withhold	
 
Based on severity of AE administer corticosteroids
 
	
 
Ensure adequate evaluation to confirm etiology or exclude other causes
 

	Grade 3	Withhold or discontinue based on the event e		
	Recurrent Grade 3 or Grade 4	Permanently discontinue		

irAEs	Toxicity Grade (CTCAE v5.0)	Action With Pembrolizumab + all IO Drugs	Corticosteroid and/or Other Therapies	Monitoring and Follow-up

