
AE(s)=adverse event(s); ALT= alanine aminotransferase; AST=aspartate aminotransferase; CTCAE=Common Terminology Criteria for Adverse Events; DRESS=Drug Rash with Eosinophilia and Systemic Symptom; GI=gastrointestinal; IO=immuno-oncology; ir=immune related; IV=intravenous; SJS=Stevens-Johnson Syndrome; T1DM=type 1 diabetes mellitus; TEN=Toxic Epidermal Necrolysis; ULN=upper limit of normal.
				

Note: Non-irAE will be managed as appropriate, following clinical practice recommendations.
 
a AST/ALT: >3.0 to 5.0 x ULN if baseline normal; >3.0 to 5.0 x baseline, if baseline abnormal; bilirubin: >1.5 to 3.0 x ULN if baseline normal; >1.5 to 3.0 x baseline if baseline abnormal
 
b AST/ALT: >5.0 to 20.0 x ULN, if baseline normal; >5.0 to 20.0 x baseline, if baseline abnormal; bilirubin: >3.0 to 10.0 x ULN if baseline normal; >3.0 to 10.0 x baseline if baseline abnormal
 
c AST/ALT: >20.0 x ULN, if baseline normal; >20.0 x baseline, if baseline abnormal; bilirubin: >10.0 x ULN if baseline normal; >10.0 x baseline if baseline abnormal
 
d The decision to withhold or permanently discontinue pembrolizumab or its IO combination partner is at the discretion of the investigator or treating physician. If control achieved or <math>\leq</math> Grade 2, pembrolizumab or its IO combination partner may be resumed.
 
e Events that require discontinuation include but are not limited to: encephalitis and other clinically important irAEs (eg, vasculitis and sclerosing cholangitis).
				

CT**Table 7 Pembrolizumab Infusion Reaction Dose modification and Treatment Guidelines**

NCI CTCAE Grade	Treatment	Premedication at Subsequent Dosing
Grade 1 Mild reaction; infusion interruption not indicated; intervention not indicated	Increase monitoring of vital signs as medically indicated until the participant is deemed medically stable in the opinion of the investigator.	None

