### Assessment of intensity/toxicity

- An event is defined as “serious” when it meets at least 1 of the predefined outcomes as described in the definition of an SAE, not when it is rated as severe.
- 1. The investigator will make an assessment of intensity for each AE and SAE (and other reportable safety event) according to the NCI Common Terminology for Adverse Events (CTCAE), version 5. Any AE that changes CTCAE grade over the course of a given episode will have each change of grade recorded on the AE CRFs/worksheets.
  - Grade 1: Mild; asymptomatic or mild symptoms; clinical or diagnostic observations only; intervention not indicated.
  - Grade 2: Moderate; minimal, local or noninvasive intervention indicated; limiting age-appropriate instrumental activities of daily living (ADL).
  - Grade 3: Severe or medically significant but not immediately life-threatening; hospitalization or prolongation of hospitalization indicated; disabling; limiting self-care ADL.
  - Grade 4: Life threatening consequences; urgent intervention indicated.
  - Grade 5: Death related to AE.

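### On the protocol's printed grade scale, a grade 3+ endocrine event controlled on continuing hormone replacement would still count as TOX, so the replacement part of the Section 7.0 exemption may do little

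*Combined protocol and SAP*

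**What the plan says.** Section 7.0 defines TOX as "any grade 3 or higher adverse event that is possibly, probably, or related to therapy received on this protocol". It then sets apart one group: "Any grade 3 or higher adverse event that is potentially treatable with steroids or hormonal replacement". Events in this group can leave the count if they resolve quickly, because the plan says that each of them "will only count as an extreme toxicity if it does not improve to grade 1 or better within 2 weeks of therapy". TOX is counted over 24 weeks from the start of combination therapy. It is compared with boundaries at 10, 20 and 35 patients, and again in the final claim at 50. The plan calls these criteria non-binding.

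Appendix 5 (Assessment of intensity/toxicity) grades events "according to the NCI Common Terminology for Adverse Events (CTCAE), version 5" and prints a general scale. Two of its levels matter here. The lower one reads "Grade 1: Mild; asymptomatic or mild symptoms; clinical or diagnostic observations only; intervention not indicated", and the next one up begins "Grade 2: Moderate; minimal, local or noninvasive intervention indicated".

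Table 6 (Section 5.2.4) deals with individual endocrine events. Hypothyroidism of grade 2, 3 or 4 is listed as continue, with the instruction "Initiate thyroid replacement hormones (eg, levothyroxine or liothyronine) per standard of care". Footnote d covers type 1 diabetes or hyperglycemia, grade 3-4 hypophysitis and grade 3-4 hyperthyroidism. Once control is achieved or the event is at grade 2 or below, it says that "pembrolizumab or its IO combination partner may be resumed".

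**The concern.** The exemption names hormone replacement, so it is evidently meant to keep well-controlled endocrine events out of the stopping count. Replacement is often continuing treatment, and a patient who still needs it has an intervention indicated. On the printed scale that describes grade 2, not grade 1. The test for the exemption therefore asks for a state that the printed scale appears to withhold from the very events the exemption names.

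These events are foreseeable here. TOX covers any therapy given on the protocol. Mitotane is adrenolytic and is intended to lower cortisol, and Table 6 lists thyroid, pituitary and diabetic events. Two investigators could classify the same controlled patient differently, and that count feeds three interim looks and the final conclusion.

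**Working it through.** **Step 1: the wording, side by side.**
- Entry to TOX: related and grade 3 or higher. Events of grade 1-2, including those on replacement, never enter.
- Exit from TOX: treatable with steroids or hormone replacement, and down to grade 1 or better within 2 weeks.
- Printed scale: no intervention indicated at grade 1; intervention indicated at grade 2.
- Result: an event that entered at grade 3+ and is controlled on continuing replacement meets the printed description of grade 2 at best, so it does not exit.
- Gap: no section says how to grade an event that is asymptomatic on stable replacement.

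**Step 2: reproduce the design.** Inputs from Section 7.0: λ = 0.5, α = 1, N = 50, prior Dir(0.15, 0.08, 0.35, 0.42). The marginal priors are Beta(0.23, 0.77) for response and Beta(0.5, 0.5) for toxicity. Stop if Pr(p_eff > 0.23 | data) < 0.5(n/50), or if Pr(p_tox ≤ 0.5 | data) < 0.5(n/50)^(1/3).

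| n | response cutoff | toxicity cutoff | stop if responses ≤ | stop if toxicities ≥ |
|---|---|---|---|---|
| 10 | 0.100 | 0.292 | 0 | 6 |
| 20 | 0.200 | 0.368 | 3 | 11 |
| 35 | 0.350 | 0.444 | 7 | 18 |
| 50 | 0.500 | 0.500 | 11 | 25 |

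These match the plan's boundary table. At n = 50, 25 toxicities give a posterior equal to the cutoff, and the plan treats that tie as unacceptable.

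Exact enumeration of the four-outcome multinomial over the four analyses gives:

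| Scenario | Acceptable, computed | Acceptable, stated | Early stop, computed | Early stop, stated |
|---|---|---|---|---|
| 0.23 / 0.50 / 0.15 | 9.56% | 9.47% | 83.4% | 83.15% |
| 0.30 / 0.30 / 0.18 | 71.91% | 71.38% | 23.8% | 24.46% |

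With 10,000 simulations, the standard errors of the stated acceptance rates are √(0.0947 × 0.9053 / 10,000) = 0.3 points and √(0.7138 × 0.2862 / 10,000) = 0.45 points. The differences, 0.09 and 0.53 points, are consistent with simulation error.

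**Step 3: sensitivity.** Let d be the share of patients who count as TOX only because a controlled, replacement-treated grade 3+ endocrine event cannot exit. The documents give no such rate, so d is an assumption. Suppose that 0.30 excludes these events, and that they arise independently of response among the 70% without other TOX. Then p_tox = 0.30 + d and p_efftox = 0.18 + 0.12 × d/0.70, with p_eff = 0.30.

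| d | p_tox | Claim acceptable | Early stop |
|---|---|---|---|
| 0 | 0.30 | 71.9% | 23.8% |
| 0.02 | 0.32 | 69.8% | 25.9% |
| 0.03 | 0.33 | 68.5% | 27.2% |
| 0.05 | 0.35 | 65.3% | 30.3% |
| 0.10 | 0.40 | 53.5% | 41.2% |

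Placing all the added events in responders, or all in non-responders, changes the acceptance rate little: 68.2% to 68.5% at d = 0.03, and 51.4% to 54.0% at d = 0.10.

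If 0.30 already includes these events, no shift applies and the first row stands.

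**The case against.** The strongest reply is that nothing shows grade 1 to be out of reach. Appendix 5 prints only a general scale. Grading follows CTCAE v5, whose endocrine criteria are not reproduced. Section 7.0 itself presumes that replacement-treatable events can reach grade 1. The general instructions of Table 6 start the steroid taper at grade 1 or below and run it for at least 4 weeks, so the protocol does use grade 1 while treatment continues. This stands in part: a reader might infer that the exemption can never apply, and the documents do not prove that. But the taper concerns time-limited steroid treatment, not continuing replacement, so the conflict in wording remains.

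A reader might also infer that Table 6 contradicts Section 7.0. It does not. Table 6 governs whether treatment is held or continued, Section 7.0 defines a monitoring endpoint, and the two may use different thresholds. Footnote d does not cover hypothyroidism, and adrenal insufficiency has no row of its own. The contrast shows only that a controlled endocrine event is judged differently in the two places.

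On size, Sections 4.2.1 and 4.2.3 report serious or severe events of all kinds in 13% of patients on pembrolizumab alone. A d of 0.10 from controlled endocrine events alone is therefore high, although mitotane could add events and no figure is given for that.

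Finally, it is tempting to say that the rule also errs the other way, because a steroid-treated event that resolves quickly escapes TOX even where Table 6 ends pembrolizumab for good. Exempting rapidly reversible events is an explicit choice of the plan. Counting every permanent discontinuation would also bring in recurrent grade 2 pneumonitis and grade 2 myocarditis, below the grade 3 floor. I do not press that change.

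**Conclusion.** The point holds as a conflict of wording in a stopping endpoint. On the literal text, a related grade 3+ endocrine event that is controlled but still needs replacement counts as TOX, and the replacement part of the exemption has little or no effect.

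It reaches no further than that. A reader might infer that all controlled endocrine events count, or that routine steroid replacement with mitotane does. Neither follows, because only related events that reached grade 3+ can enter. The exemption still works for steroid-treated events that fall to grade 1 in time.

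The loss in the chance of claiming acceptability is about 2 points at d = 0.02, 3 at 0.03, 7 at 0.05 and 18 at 0.10. It depends on an assumed d and on 0.30 having been set without these events. If 0.30 includes them, the stated power does not change. Because the criteria are non-binding, a boundary crossed on such events need not end the trial.

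**What to change.** In Section 7.0, reword the counting rule so that a grade 3+ endocrine event treated with hormone replacement counts as TOX only if it is not controlled on replacement (grade 2 or better) within 2 weeks of starting it. Keep the grade 1 criterion for steroid-treated non-endocrine events. Reconcile the wording with the general instructions and footnote d of Table 6 and with the scale in Appendix 5. This changes endpoint counting only, not any rule for holding or resuming treatment.

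State also that the rates 0.30 and 0.50 were set under this same definition. This matters in both directions. If 0.50 was set with such events counted, and 5 per 100 (assumed) then drop out, the probabilities become p_eff = 0.23, p_tox = 0.45 and p_efftox = 0.15 × 0.45/0.50 = 0.135. The chance of claiming acceptability then rises from 9.56% to 18.55%. If the rates were set under another definition, they should be restated and the operating characteristics rerun.

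The cost is one or two sentences. The boundaries and sample size do not depend on the TOX wording while 0.30 and 0.50 stand. The downside is that slightly fewer events count toward the toxicity boundary, though all adverse events are still tabulated by highest grade.
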